#### 8.2 STATISTICAL ANALYSIS

#### 8.2.1 Included and evaluable population

The absolute and relative frequency of patients who meet all the inclusion criteria and do not meet any of the exclusion criteria will be presented.

The frequency distribution of the sub-population of non-evaluable patients will be presented depending on the reasons for non-evaluation:

- Patients who are not 18 years or older diagnosed with metastatic RCC who, in the investigator's opinion, are candidates for starting first-line treatment with a tyrosine kinase inhibitor according to routine clinical practice.
- Patients with contraindication for treatment with a tyrosine kinase inhibitor
- Patients without a baseline ECOG of less than or equal to 2
- Patients who does not give their signed and dated informed consent
- Patients not committed and able to complete the quality of life questionnaires and the patient diary
- Patients who are not candidates for first-line treatment with a tyrosine kinase inhibitor
- Patients who are receiving the treatment as second-line or subsequent therapy
- Patients with untreated hypothyroidism
- Patients with untreated severe anaemia
- Pregnant or breastfeeding patients
- Patients who have had a myocardial infarction or stroke (CVA) within the last 6 months
- Patients with severe hepatic impairment.
- Patients concomitantly using potent inhibitors or inducers of hepatic cytochrome CYP3A4.

#### 8.2.2 Descriptive analysis

The mean value, standard deviation, median, minimum, maximum, interquartile range (IR) and 95% confidence interval (95%CI) will be given for:

Patients' age at baseline visit

- Time elapsed since the disease diagnosis moment (calculated as the difference between the disease diagnosis date and the baseline visit date)
- Time elapsed since the advanced diagnosis (calculated as the difference between the advanced stage diagnosis data and the baseline visit date)

The frequency distribution of the patients will be presented according to:

- ✓ Gender
  - o Male
  - o Female
- $\checkmark$  ECOG at the time of diagnosis
  - o 0
  - o 1
  - o 2
  - o 3
  - o 4

✓ Heng prognostic criteria

- Favourable
- Intermediate
- Poor prognosis

 $\checkmark$  Site of metastasis

- o Lung
- o Brain
- o Nodes
- o Bone
- o Liver
- 0 Kidney
- ✓ Histological type
  - Clear cells
  - Chromophobe
  - o Sarcomatoid differentiation
    - <20%
    - **20-30%**
    - **31-50%**
    - **5**1-75%

■ >75%

- Papillary type 1
- Papillary type 2
- o Mixed
- Not performed

#### ✓ Smoking

- o No
- o Yes
- o Occasional
- $\circ$  Former smoker of <6 months
- ✓ Dose of the tyrosine kinase inhibitor and regimen with which they initiated treatment at baseline visit
  - Sunitinib 50 mg 4/2 regimen
  - Sunitinib 50 mg 2/1 regimen
  - o Sunitinib 37.5 mg 4/2 regimen
  - Sunitinib 37.5 mg 2/1 regimen
  - Sunitinib 25 mg 4/2 regimen
  - Sunitinib 25 mg 2/1 regimen
  - Pazopanib 800 mg/24 hours continuous
  - Pazopanib 400 mg/24 hours continuous
  - Sorafenib 400 mg/24 hours continuous
  - Sorafenib 400 mg/12 hours continuous

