this is a drug that is administered intermittently. Fatigue typically occurs 2-3 weeks after the start of treatment, increases in intensity during weeks 3 and 4, and tends to improve during the 2-week off-treatment period, during which patients are comparatively better than during on-treatment weeks. This has resulted in the use of alternate sunitinib scheduling in clinical practice in order to improve tolerability and maintain effective dose intensity, with the schedule of 14 days on and 7 days off being the most commonly used (2/1 schedule). Results based on the use of these schedules by different groups have recently been published (retrospective analyses). The European Association of Urology Guidelines on Renal Cell Carcinoma 2015 describe the schedule of 2 weeks on and 1 week off treatment for the management of toxicity in patients being treated with sunitinib.

It is not clear what percentage of fatigue is cancer-related and what percentage is attributable to the tyrosine kinase inhibitor as both types of fatigue are very similar and often coexist. The mechanisms of fatigue are not well described. Changes at muscle level can cause peripheral fatigue, whereas central nervous system failure to activate the motor neurons adequately would cause central fatigue.

Fatigue is more common in men, particularly in young men, resulting in repeated treatment interruptions. However, fatigue tends to decrease with increasing treatment cycles. Whether this phenomenon represents an adaptation and/or learning by the patient or a true lower incidence is unknown.

It is important to rule out other causes that may cause or exacerbate fatigue, such as dehydration, hypothyroidism, hypercalcaemia, anaemia or depression. These adverse events must be monitored every 2-3 cycles.

In the phase I study published by Faivre, asthenia was associated with an increase in daytime napping and night-time somnolence. Age and baseline status (ECOG) at the start of the study did not predict asthenia.

Patient education is crucial. It is necessary to explain that this adverse event will quite probably appear and we have strategies to manage it if it occurs.

It is interesting to see fatigue in the context of the disease and to readjust the patient's expectations, explaining that it will be necessary to adapt his/her everyday activities to save energy.

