## 4 HYPOTHESIS TESTING

The statistical significance value is set to p<0.05 The SPSS statistical package, V19.0 or later will be used.

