#### 5 ANALYSIS POPULATION

#### 5.1 FULL ANALYSIS SET

Plans are to include 100 patients in the study to receive first-line treatment over the course of 18 months at 35 sites.

This is a descriptive study; therefore, a specific number of patients is not required to calculate the sample size.

In order to study the fatigue-related quality of life of patients who are taking a tyrosine kinase inhibitor, evaluated using the validated 13-item FACIT-Fatigue scale for patients with metastatic renal cancer on Spanish, the inclusion of 100 patients with metastatic renal carcinoma who are about to receive first-line treatment with a tyrosine kinase inhibitor and who meet the screening criteria of the study is proposed.

This sample size will allow us to estimate percentages of patients with fatigue (severe/non-severe) during follow-up, with a 95% level of significance and an estimated proportion of 10%, assuming a discontinuation rate of 5%.

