## • Has taken the medication:

- In the morning (between 7 am and 12 noon)
- In the afternoon (between 1 pm and 7 pm)
- At night (between 8 pm and 6 am)
- I have not taken any medication this week

For each one of the weekly habits described above, a summary calculation will be made (after three months) of each patient's habits in terms of daytime rest, physical exercise and taking their medication, taking the options marked with greater frequency in the last 12 weeks into account.

FACIT\_Fatigue: The main measures of centrality and dispersion measures will be calculated (mean, standard deviation, median, minimum, maximum, IR and 95%CI ) from the score obtained in the FACIT\_Fatigue quality of life scale, calculated as described in ANNEX 1. The absolute and relative frequency of patients with severe fatigue, being those with a score of less than 30 points on the FACIT\_Fatigue scale, will also be presented.

For each one of the evolution visits (week 6, week 12, week 18, week 24, week 30 and week 36), a study will be performed to ascertain whether significant changes have occurred in fatigue-related quality of life versus the previous evaluation, and defined as:

- **Improvement:** if there is an increase of more than 4 points in the FACIT\_Fatigue scale score versus the previous evaluation
- **Maintenance:** if the score on the quality of life scale does not vary by more than 4 points versus the previous evaluation
- **Worsening:** if the score obtained on the Facit\_Fatigue scale decreases by more than four points versus the previous evaluation.

Significant associations will be sought between the habits of daytime rest, the practice of physical aerobic exercise, medication taken, dose and treatment schedule changes, dose interruptions and the number of days of treatment

interruption depending on the evolution in the evaluation of the fatigue in the FACIT\_Fatigue over the last six weeks. The Pearson chi-squared test will be used for this purpose (or Fisher's exact test for 2x2 tables or likelihood ratio test for mxn tables, if necessary).

- Treatment: For each one of the treatment cycles received by patients during the 9-month follow-up, the following will be studied:
  - **Dose change:** the absolute and relative frequency of patients who have changed doses since the last cycle will be provided. In the sub-population of patients with dose changes in the last cycle, their frequency distribution will be presented according to:

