#### 9 LIST OF TABLES AND TABLE OF CONTENTS

Table/Graph number			Table/Graph title					
1.			Included and evaluable population					
2.			Descriptive analysis					
	.1		Demographic and disease information					
		.1	Age					
		.2	Time from diagnosis and from the advanced diagnosis of the disease					
		.3	Gender					
		.4	ECOG at time of diagnosis, Heng prognostic criteria and site of metastasis					
		.5	Histological type					
		.6	Smoking					
	.2		Dosage and treatment regimen of tyrosine kinase with which the patient begins treatment					
3.			Analysis of evolution					
	.1		Presence of palmar-plantar erythrodysesthesia of any grade (month 3, month 6, month 9)					
		.1	Association between medication intake habits and evolution of hand- foot syndrome (every three months)					
		.2	Association between dose changes and evolution of hand-foot syndrome (every three months)					
		.3	Association between dose, treatment regimen received and the evolution of hand-foot syndrome (every three months)					
		.4	Association between temporary treatment interruptions and evolution of hand-foot syndrome (every three months)					
	.2		Presence of fatigue of any grade (baseline, month 3, month 6, month 9)					
		.1	Association between daytime rest habit and fatigue evolution (every three months)					
		.2	Association between daytime physical exercise and fatigue evolution (every three months)					
		.3	Association between daytime medication-taking habits and fatigue evolution (every three months)					
		.4	Association between daytime dose changes and fatigue evolution (every three months)					
		.5	Association between doses, daytime treatment regimen and fatigue evolution (every three months)					

CT24-GSOP-SD-GL04 NI Study SAP Template; Template Version 1.0, Effective 31-Dec-2013 Page 23 of 29

PFIZER CONFIDENTIAL

	.6	Association between temporary daytime interruptions and fatigue evolution (every three months)
	3	Data from the patient diary
	.1	Daytime rest (weekly)
	.2	Physical exercise (weekly)
	.3	Has taken the medication (weekly)
•-	4	Quality of life (FACIT_Fatigue) (every six weeks)
	.1	Association between daytime habit and evolution on the Facit_Fatigue (every six weeks)
	.2	Association between daytime physical exercise and evolution on the Facit_Fatigue (every six weeks)
	.3	Association between daytime medication-taking habits and evolution on the Facit_Fatigue (every six weeks)

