	.4	Association between daytime dose changes and evolution on the Facit_Fatigue (every six weeks)
	.5	Association between doses, daytime treatment regimen and evolution on the Facit_Fatigue (every six weeks)
	.6	Association between temporary daytime interruptions and evolution on the Facit_Fatigue (every six weeks)
.4	5	Treatment, dose changes and temporary interruptions
· ·	7	Efficacy analysis
	.1	Number of treatment cycles received
	.2	Best response rate achieved with first-line treatment
	.3	ORR, DOR
	.4	Time on treatment and time to best response
	.5	Time to Treatment Failure (TTF)
	.6	Progression-free survival (PFS)
	.7	Reason for termination of treatment and reason for death

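### The SAP's only dose/regimen coding is a ten-level list; if it is the row variable of Tables 3.1.3, 3.2.5 and 3.4.5, their tests cannot separate drug, dose and schedule

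*SAP*

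**What the plan says.** - **Coding.** SAP 8.2.2 presents "Dose of the tyrosine kinase inhibitor and regimen with which they initiated treatment at baseline visit" as a frequency distribution over ten categories: six for sunitinib (three doses, each on 4/2 or 2/1), two for pazopanib and two for sorafenib. SAP 8.2.3 repeats the list for the new dose after a dose change. Neither section defines a separate variable for drug, dose level or schedule.
- **Tables.** SAP 9 lists Table 3.1.3, "Association between dose, treatment regimen received and the evolution of hand-foot syndrome (every three months"), Table 3.2.5 (the same for CTCAE fatigue) and Table 3.4.5, "Association between doses, daytime treatment regimen and evolution on the Facit_Fatigue (every six weeks"). Dose changes have their own tables (3.1.2, 3.2.4, 3.4.4), so these three concern the regimen received.
- **Outcome and test.** SAP 8.2.3 classifies change as improved, maintained or worsened. It names Pearson's chi-squared test, with Fisher's exact test for 2x2 tables or the "likelihood ratio test for mxn tables, if necessary". It gives no rule for when the fallback becomes necessary. SAP 4 adds: "The statistical significance value is set to p<0.05".
- **Schedule.** SAP 2 and the protocol background describe alternative sunitinib scheduling as a response to fatigue, "with the schedule of 14 days on and 7 days off being the most commonly used (2/1 schedule"). Protocol secondary objective 4 includes the impact of off-treatment periods on fatigue and hand-foot syndrome. The SAP's version of that objective leaves this item out. Neither document states a 4/2 versus 2/1 hypothesis.

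**The concern.** Drug, dose level and schedule are three different questions. Crossed into one unordered variable, they are tested together. A significant result would not say which of the three was responsible. A non-significant one would say little, because the test spreads its sensitivity over up to 18 degrees of freedom.

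Schedule suffers most. Each schedule is divided over three sunitinib dose rows, and the pazopanib and sorafenib rows carry no 4/2 versus 2/1 information. Yet among the listed regimens, schedule is what distinguishes one pattern of planned off-treatment time from another, and this is the item named in protocol secondary objective 4. No planned analysis isolates it.

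**Working it through.** **1. What the sample size supports.** SAP 5.1 states "Plans are to include 100 patients in the study", a 95% level, a proportion of 10% and 5% discontinuation, but no precision. Evaluable patients: 100 x 0.95 = 95. The 95% half-width is 1.96 x √(0.10 x 0.90 / 95) = 0.060. Working backwards, a precision of 6 points needs 1.96² x 0.09 / 0.06² = 96.04, so 97 patients, and 97 / 0.95 rounds up to 103. Precisions of 5 and 7 points give 147 and 75. So 100 fits an unstated precision of about 6 points for one percentage. It is no basis for an association test.

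**2. Shape of the table.** Ten rows by three columns give (10 − 1) x (3 − 1) = 18 df. With 95 patients that is 95 / 10 = 9.5 per row and 95 / 30 = 3.2 per cell. Under four assumed drug mixes, 21 to 30 of the 30 cells have an expected count below 5. Empty rows reduce the df: in simulation the average was about 14–17.

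**3. Power by formula.** Assume 70% sunitinib, split evenly by schedule, other TKIs midway between the two schedules, and no effect of drug or dose. Sunitinib patients: 0.70 x 95 = 66.5. Take improved/maintained/worsened as 15/35/50% on one schedule and 25/50/25% on the other, with mean 20/42.5/37.5%. The noncentrality is

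λ = 66.5 x (0.05²/0.20 + 0.075²/0.425 + 0.125²/0.375) = 66.5 x 0.0674 = 4.48.

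Under these assumptions λ is the same for the ten-level table and for the direct sunitinib 2 x 3 table. Only the df differ:

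| Worsened, by schedule | λ | Direct, 2 df | Ten-level, 18 df | Relative loss |
|---|---|---|---|---|
| 50% v 25% | 4.48 | 0.46 | 0.18 | 60% |
| 40% v 20% | 3.25 | 0.35 | 0.14 | 60% |
| 55% v 20% | 9.05 | 0.77 | 0.38 | 51% |

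With 85% sunitinib and 55% v 20%, power falls from 0.85 to 0.47 (45% loss).

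**4. Power by simulation.** Assumptions: 60–90% sunitinib, schedules even, sunitinib doses split 70/20/10, and improved/maintained/worsened 15/40/45% on 4/2, 30/50/20% on 2/1 and 22/45/33% on other TKIs. The numbers contributing are also assumed.

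| n | Ten-level Pearson | Direct 4/2 v 2/1 |
|---|---|---|
| 93 | 15–25% | 46–63% |
| 69 | 11–19% | 33–51% |
| 55 | 8–14% | 29–41% |

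Pairing the ends of the ranges, the loss runs from 1 − 25/63 = 60% to 1 − 8/29 = 72%.

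**5. Error rate under the null.** On the ten-level table Pearson rejects in about 2.5–5% of null studies. The likelihood-ratio test rejects in about 7–12%. The direct 2 x 3 Pearson test stays at about 4–6%.

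**6. Precision of the direct contrast.** With 33.25 patients per schedule and worsening of 50% v 25%, the 95% half-width for the difference is 1.96 x √((0.25 + 0.1875)/33.25) = 0.22. The interval would be about 22 points either side of a 25-point difference.

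**The case against.** The strongest reply is that the SAP never says the ten-level list is the row variable. The list appears as a baseline frequency table and again for new doses after a change. The association text in 8.2.3 speaks of dose and schedule changes, and the table titles put a comma between dose and regimen, which could mean two variables. This stands, so the point is conditional. If another coding is meant, however, it is undefined, and the same edit is needed.

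A reader might infer that the schedule question cannot be answered from this study. The documents do not support that. Every sunitinib category carries its schedule, so the rows can be collapsed without new data. Only the overall p-value fails to isolate schedule.

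A reader might also treat 4/2 versus 2/1 as a study hypothesis. It is not one: the study calls itself descriptive and states no power for any association. The contrast earns its place only through the off-treatment item in the protocol objective and the rationale.

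Three limits of the direct contrast also stand:

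- **Power depends on an even split.** With schedules split 80/20, simulated direct power falls to 30–47% at n = 93 and 18–28% at n = 55.
- **Pooling over dose does not remove dose.** In an illustration with no schedule effect, the outcome difference placed on dose, and lower doses in 60% v 10% of the two schedule groups, the pooled test rejected in 13–18% of runs. Physician choice of schedule adds further confounding.
- **Separate factors mean more tests.** SAP 8.2.3 has 2 hand-foot, 3 fatigue and 6 FACIT change evaluations, so 11 tests. Drug plus schedule gives 22. Adding dose within each of three TKIs gives up to 11 x 5 = 55, all at unadjusted 0.05.

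**Conclusion.** The point holds as a conditional one. The SAP's only coding of dose and regimen mixes three questions. If it is used in these three tables, the overall test cannot be attributed to drug, dose or schedule, and the tables are too sparse for the fallback test to keep its level.

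The loss of roughly half to two-thirds of the power for the schedule contrast rests on assumed drug mix, schedule split, dose split, effect size and numbers remaining. None of these is in the documents. To say as fact that most of the power is lost would go too far. The sparsity and the problem of attribution do not depend on the effect assumptions.

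The change is worth making before analysis. It makes the result interpretable, though not well powered: about 29–63% for the direct contrast under the simulation assumptions, and less if one schedule dominates. A non-significant schedule result would remain weak evidence, which is why an estimate with an interval matters more than the p-value.

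**What to change.** For Tables 3.1.3, 3.2.5 and 3.4.5, name the row variables and take each at the start of the interval over which change is measured:

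1. TKI: sunitinib, pazopanib or sorafenib.
2. Within sunitinib only, schedule 4/2 versus 2/1. Report an estimate with a 95% CI, for example the difference in the proportion worsened, and show it by dose level as well so that dose imbalance is visible.
3. Listed dose level within each TKI, tested only where group size allows and otherwise described.

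Use exact or Monte Carlo p-values for sparse tables in place of the likelihood-ratio fallback. Label the results exploratory and observational, since the physician chooses the schedule. Keep the ten-category list as a descriptive frequency table.

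The cost is SAP wording and table shells; the data are already recorded. The downside is a few more exploratory tests, which item 3 limits, and a schedule contrast that is clearer but still imprecise.

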## 8.2.3 Follow-up analysis

The evolution of the following aspects will be presented for each one of the follow-up visits of the patients at which the variables listed below are recorded:

- Presence of palmar-plantar erythrodysesthesia: the absolute and relative frequency of patients who as of month 3 of treatment develop palmar-plantar erythrodysesthesia of any grade will be provided. In the sub-population of patients with hand-foot syndrome, the frequency distribution will be presented according to the degree of severity of these AE, according to CTCAE (Common Terminology Criteria form Adverse Event) version 4:
  - o Grade 1
  - o Grade 2

#### o Grade 3

For each one of the evolution visits (month 6 and month 9), a study will be performed to ascertain whether significant changes have occurred in the presence and the grade of the HFS with regard to the previous visit, defined as (improved, maintained or worsened). The Pearson chi-squared test will be used for this purpose (or Fisher's exact test for 2x2 tables or likelihood ratio test for mxn tables, if necessary).

- Presence of fatigue: the absolute and relative frequency of patients with the presence of fatigue of any degree since the baseline visit will be provided. In the sub-population of patients with fatigue, the frequency distribution will be presented according to the degree of severity, according to CTCAE (Common Terminology Criteria form Adverse Event) version 4:
  - o Grade 1
  - o Grade 2
  - o Grade 3
  - o Grade 4

For each one of the evolution visits (month 3, month 6 and month 9), a study will be performed to ascertain whether significant changes have occurred in the grade of fatigue with regard to the previous visit, defined as (improved, maintained or worsened). Significant associations will be sought between the habits of daytime rest, physical aerobic exercise, medication taken, dose and treatment schedule changes, dose interruptions and the number of days of treatment interruption depending on the evolution of the presence and degree of fatigue in the last twelve weeks. The Pearson Chi-squared test will be used for this purpose (or Fisher's exact test for 2x2 tables or likelihood ratio test for mxn tables, if necessary).

- Patient diary data (weekly): the distribution of patient frequencies will be presented according to the following habits:
  - Napping
    - Every day
    - Weekend and/or holidays
    - Sporadically, between 2 or 6 days
    - Has not taken a nap any day

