3. ABSTRACT

Prospective, multicentre, observational study in patients with metastatic renal cell carcinoma (mRCC) receiving a tyrosine kinase inhibitor as first-line treatment according to routine clinical practice, designed to evaluate the incidence of fatigue and hand-foot syndrome in order to determine how these affect the baseline characteristics of the patient and his/her disease (age, gender, baseline status, tumour histology, etc.) and the patient's lifestyle as such side effects develop.

[figure not shown]
STUDY TITLE

Prospective, multicentre, observational study on fatigue- and hand-foot syndrome-related quality of life in patients with metastatic renal cell carcinoma receiving a tyrosine kinase inhibitor as first-line treatment (TROYA Study)

PROTOCOL CODE: A6181218 (PFI-ITK-2015-01) TROYA

COORDINATING INVESTIGATOR:

The scientific coordinator will be responsible for maintaining the methodological rigour of the study, both in the design phase and in the evaluation of results and writing of the final report. He will guarantee the ethical conduct of the study, maintaining scientific support for all participating doctors until the results are published.

STUDY SITES:

It is initially considered optimal to include patients at approximately 35 Spanish sites (see ANNEX 7 to the protocol, which contains the list of proposed sites).

IEC THAT WILL ASSESS THE STUDY

IEC of Navarre

Secretary of the Independent Ethics Committee of Navarre (IEC) [name]

[contact] [contact] Email: [contact]

STUDY OBJECTIVES

PRIMARY OBJECTIVE

Fatigue-related quality of life of patients receiving a tyrosine kinase inhibitor evaluated using the validated 13-item FACIT-Fatigue scale for patients with metastatic renal cancer in Spanish.^{1,2}

SECONDARY OBJECTIVES

- 1) Quality of life in patients with palmar-plantar erythrodysaesthesia (hand-foot syndrome).
- 2) To assess the following adverse effects according to version 4 of the CTCAE (Common Terminology Criteria for Adverse Events): any grade of fatigue and hand-foot syndrome (HFS).
- 3) To study what role aerobic exercise (walking quickly, running, swimming, playing tennis, dancing and/or riding a bike) plays in the onset of fatigue before starting and during treatment.

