Any adverse events experienced by the patient will be recorded according to clinical practice, in compliance with the toxicity manuals of the National Cancer Institute Common Terminology Criteria for Adverse Events version 4.0.

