#### TREATMENT

- 1) Time when the oral treatment is taken
- 2) Tyrosine kinase inhibitor dose and treatment regimen
- 3) Number of dose changes per treatment cycle
- 4) Temporary treatment interruptions, number of interruptions per treatment cycle
- 5) Best response achieved with first-line treatment
- 6) Mean duration of treatment
- 7) Time to treatment failure
- 8) How long each patient stays on first-line treatment/no. of cycles received
- 9) Reason for discontinuing the first-line drug
- 10) Date of disease progression and/or death

Through the analysis of the collected variables the following aspects will be assessed:

- **Progression-Free Survival (PFS):** defined as the interval from the start of treatment to the date of the first documentation of objective tumour progression or death from any cause.

- **Objective Response Rate (ORR):** Defined as the proportion of subjects who achieve complete remission (CR) or partial response (PR). In addition, subjects with stable disease (SD) will also be evaluated to obtain clinical benefit along with subjects with tumour progression. Subjects will be evaluated according to RECIST 1.1.

- **Duration of response (DOR):** in patients with PR or CR, it will be defined as the interval from the date the response is documented to the first date that progressive disease is observed.

- **Safety:** The safety of the tyrosine kinase inhibitor will be evaluated describing the incidence and all grades in the event of fatigue and or hand-foot syndrome.

- **Fatigue-related quality of life of patients:** this will be measured based on the results obtained after completion of the FACIT-Fatigue questionnaire by the patient.

- **HFS-related quality of life of patients** in cases in which HFS is present with a score from 1 to 3 according to version 4 of the CTCAE (Common Terminology Criteria for Adverse Events).

- Date of disease progression and/or death.

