#### 6.2 SAFETY OBJECTIVES

- **Safety:** the safety of the tyrosine kinase inhibitor will be evaluated by describing the incidence of serious adverse events, the side effects included in the potential drug risk management plan and all CTCAE grades if fatigue and/or hand-foot syndrome are present.

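### The SAP promises HFS incidence and grades, but its only specified HFS tabulation starts at month 3 and yields neither cumulative incidence nor worst grade per patient

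*SAP*

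**What the plan says.** The Protocol abstract describes the study as "designed to evaluate the incidence of fatigue and hand-foot syndrome", and secondary objective 2 covers any CTCAE grade of both effects.

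The SAP makes two general commitments. Section 6 (list of treatment variables) says safety will be "evaluated describing the incidence and all grades in the event of fatigue and or hand-foot syndrome". Section 6.2 sets out the task as "describing the incidence of serious adverse events, the side effects included in the potential drug risk management plan and all CTCAE grades" where fatigue or HFS is present. Neither has a month-3 limit. Neither gives a time window, a denominator or a method.

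The operational rule is in SAP 8.2.3, which gives the frequency of "patients who as of month 3 of treatment develop palmar-plantar erythrodysesthesia of any grade" and then the grade distribution among those affected. Change in HFS is tested "For each one of the evolution visits (month 6 and month 9"), each time against the previous visit. SAP section 9, table 3.1, matches: "Presence of palmar-plantar erythrodysesthesia of any grade (month 3, month 6, month 9").

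Fatigue is handled differently in the same section. The SAP counts "patients with the presence of fatigue of any degree since the baseline visit will be provided", tests change at months 3, 6 and 9, and includes baseline in the table.

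Data collection is wider than the HFS analysis. Protocol 7.2 states: "Any adverse events experienced by the patient will be recorded according to clinical practice". The table in Protocol section 9 puts all non-serious adverse events on the CRF, and the reporting period there runs from first dose to at least 28 days after the last dose.

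**The concern.** Incidence means the share of treated patients who ever have the event, and for a toxicity it is normally reported with each patient's worst grade. A table that begins at month 3 and is organised by visit does not give that unless the SAP says what period each visit looks back over, and it does not say.

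The patients most exposed to omission are those whose HFS came early and settled, and those who stopped treatment before a month-3 assessment. The documents make early resolution plausible: secondary objective 4 treats dose reductions and temporary breaks as possible means of controlling HFS, and the cited pivotal sunitinib trial had 38% temporary interruptions and 50% dose reductions.

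At stake are the HFS part of secondary objective 2 and, to a lesser degree, objective 4. Because HFS change is tested only from month 6, the first three months have no specified HFS change to relate to dose changes or interruptions.

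**Working it through.** **Is there a plan figure to reproduce?** No. The documents state no expected HFS incidence or precision. The sample-size statement (100 patients, 10% proportion, 5% discontinuation) concerns fatigue. The only HFS rate is 9% for grade 3-4 in the cited sunitinib trial, with no onset time.

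**Does another planned output fill the gap?** SAP section 9 lists HFS by visit (3.1), HFS association tables (3.1.1 to 3.1.4), and tables for fatigue, diary, FACIT, treatment and efficacy. It has no adverse event table, no cumulative HFS incidence, no worst grade per patient and no HFS result at discontinuation. The end of 8.2.3 plans paired comparisons of HFS with baseline, yet table 3.1 has no baseline entry. A programmer working from 8.2.3 and section 9 would not produce what sections 6 and 6.2 promise.

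**What does each reading of the month-3 wording return?** Let I be the true incidence over 9 months, f the share of onsets before month 3, and r the share of those resolved or off study by month 3. All values below are assumptions, with I = 30%.

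*Reading 1, onset from month 3.* Reported = I(1 − f). Under a constant hazard, f = (1 − 0.70^(3/9))/0.30 = 0.374.
- f = 0.374: 0.30 × 0.626 = 18.8%
- f = 0.5: 15.0%
- f = 0.8: 6.0%

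*Reading 2, present at the visit.* Reported = I(1 − f·r), with f = 0.5. This credits every later onset as caught, which is generous to the plan.
- r = 0.25: 26.3%
- r = 0.5: 22.5%
- r = 0.75: 18.8%

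*Reading 3, any HFS since the previous assessment.* Nothing is lost in patients who attend. Let s be the share of all patients who have HFS but no month-3 assessment. With s = 5%:
- over all patients: 0.30 − 0.05 = 25.0%
- over attenders, if those 5% are the only absentees: 0.25/0.95 = 26.3%

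The direction on reading 3 is not fixed if the denominator is attenders. If 17% were not assessed and only 2 points of those had HFS, the result would be (0.30 − 0.02)/(1 − 0.17) = 33.7%, above the true 30%. The three interval counts also cannot be added to give a cumulative figure, because one patient can appear in more than one.

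**What would a from-first-dose count return?** Over all treated patients it returns I itself, provided the events are recorded.

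**The case against.** The strongest defence is that reading 3 is the natural one. SAP 8.2.3 presents results for each follow-up visit, and month 3 is the first scheduled visit after baseline. Table 3.1 includes month 3, which fits poorly with excluding weeks 1 to 12. The verb in 8.2.3 denotes onset. Fatigue evolution in the same section looks back twelve weeks. The contrast with fatigue also has a rationale: fatigue can be cancer-related and so present at baseline, whereas HFS is introduced as a side effect of treatment. This defence stands to the extent that it makes reading 3 plausible. It does not make it stated, and even on reading 3 there is no cumulative incidence or worst grade per patient.

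A reader might infer three stronger things, none of which the documents support.

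- **That the SAP restricts HFS incidence to month 3 onward.** Sections 6 and 6.2 carry no such limit. What is missing is their implementation.
- **That early HFS is lost.** All non-serious adverse events go on the CRF and safety reporting starts at first dose. Additional visits may also be recorded. The discontinuation assessment belongs to the questionnaire schedule, and no HFS analysis is tied to it.
- **That the documents give the size of the loss.** Exponential PFS at the cited medians gives 1 − 0.5^(3/11) = 17.2% and 1 − 0.5^(3/9.2) = 20.2% progressing or dying before month 3. That is not a rate of missed HFS, and the 9.2-month median comes from a mixed naive and pretreated population. The 8% and 19% stopping sunitinib are for side effects in general, at any time, not for HFS before month 3.

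**Conclusion.** The point holds as a gap between what the SAP promises for HFS and what it specifies. Two of the three readings of the month-3 wording understate incidence. The third captures early resolved HFS in attenders, but leaves out patients without a month-3 assessment and gives neither cumulative incidence nor worst grade.

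The size is unknown. The illustrative ranges for a true 30% (6% to 19% on reading 1 and about 19% to 26% on reading 2) rest entirely on assumed onset and resolution patterns. They show that the choice of reading matters; they do not estimate the bias in this study. A downward bias should not be stated as fact, because it depends on the reading. The result affected is secondary and descriptive, but it is part of the study's declared purpose.

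**What to change.** - In SAP 8.2.3, define HFS incidence by the worst CTCAE grade per patient, with grade 0 included, from first dose to the end of the safety reporting period. Take it from the adverse event records, with all patients who took at least one dose as the denominator.
- Relabel the month 3, 6 and 9 tables as by-visit results, state the look-back period, and show the number assessed at each visit.
- Add the same worst-grade summary for CTCAE fatigue. Fatigue is already counted since baseline, so show the baseline grade separately.
- Add these tables to SAP section 9 so that sections 6 and 6.2 have a matching output.

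The cost is one or two extra tables and a few sentences. This assumes that the adverse event pages hold grade and onset date; the CRF (Protocol Annex 2) was not available to check. On that assumption no new data are needed, and this is a cheap improvement.
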